**Participants.** Veterans ( $n \approx 48$ , potential range 24-60) will be recruited from medical (e.g., primary care) and mental health programs throughout the facility and from the community. Given the feasibility aim of this project, ability to participate is intentionally broad to demonstrate demand and maintain ecological validity. Thus, inclusionary criteria are as follows: (1) self-identified as a BIPOC, (2) Veteran, (3) age 18 or older, (4) able to consent to study activities, and (5) endorsing one or more perceived discrimination experiences on the *Everyday Discrimination Form* (short version) or the *Major Experiences of Discrimination Scale* (abbreviated version; Sternthal, Slopen & Williams, 2011) "a few times a year" or more frequently and endorsing stress on a validated single-item measure (Elo, Leppanen, & Jahkola, 2003). Exclusionary criteria include: (1) serious mental illness, alcohol/substance use disorders, or cognitive impairment that may interfere with the ability to benefit from group (e.g., severe depression, psychotic illness, mania, dementia, **untreated** alcohol/substance dependence); and (2) serious suicidality or homicidality (e.g., ideation with plan/intent) that is likely to require urgent/emergent intervention within the study period.

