**Acceptability, appropriateness and feasibility.** Relevant to aim 2, participant behavior is one important marker of participants' perceptions of the project and their ability to comply with research procedures. *Retention rate* will be defined as the percent of enrolled sample completing all assessment time points; at least 80% completion will be considered successful. *Per protocol completion rate* will be defined as the proportion of subjects who complete 6 or more sessions among those who initiate treatment; at least 90% completion will be considered successful. *Intent-to-treat completion rate* will be defined as the proportion of subjects who complete 6 or more sessions of intervention among all randomized subjects; at least 80% is the target. *Compliance with homework* will be assessed with a goal of at least 80% moderately or fully complete (refer to **Assessment approach**). In addition, Veterans will be directly queried about their experience using the *Acceptability of Intervention Measure (AIM)*, *Intervention Appropriateness Measure (IAM)*, and *Feasibility of Intervention Measure (FIM)*. The 5-item measures have strong content validity, test-retest reliability and sensitivity to change (Weiner et al., 2017). The psychotherapy version of the *Provider Rating Scales*, which were previously used to assess perceptions of VA mental health providers (Spoont et al., 2017), will be used to assess Veterans' perceptions of the group leader. Between-group differences on these measures would likely reflect the difference in content between the two groups.

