**Sample size.** As a feasibility study, the decision about sample size is not about establishing sufficient power to detect change in clinical outcomes but rather about demonstrating the viability of a future larger-scale study. The sample size was determined based on practical and quantitative considerations. We will aim for enrollment of 4 groups of each type of intervention, each with approximately 6 Veterans (average 6, range 4-10), leading to a total sample size of approximately 48 (24/cell) in the 15-month recruitment period. This rate of enrollment would demonstrate feasibility of a larger future study in that we would demonstrate that a steady flow of adequately sized intervention groups can be recruited. Given that this is a pilot and feasibility study, we are looking for clinical signal and feasibility rather than examining efficacy. All sample size analyses were performed using statistical package R. A two-sided type I error of 0.05 was assumed.

The sample size assessment was conducted for assessing the enrollment and completion rates. First, we assessed the precision of estimates based on projected sample size. We considered a range of target rate from 0.60 to 0.90 and estimated the width of the 95% exact binomial confidence interval for enrollment and completion rates for overall and for each intervention group (see **Table 1**).

**Table 1.** The width of 95% confidence intervals for enrollment and completion rates

Sample size	Estimated rate						
	0.60	0.65	0.70	0.75	0.80	0.85	0.90
48	0.267	0.261	0.251	0.239	0.222	0.201	0.174
24	0.365	0.357	0.345	0.329	0.308	0.282	0.249

From **Table 1**, if an estimated intervention initiation rate is 0.80, a sample size of 48 (total) and 24 (per intervention group) will produce a two-sided 95% confidence interval with a width of 0.222 and 0.308,

respectively. If an estimated intervention initiation rate is 0.90, the width of the 95% CI is reduced (becomes more precise, see **Table 1**) with the same sample size projected above.

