We will assess four outcome measures for enrollment and retention: 1) *enrollment rate* defined as the proportion of consented subjects among all screened and eligible patients; 2) *initiation rate* defined as the proportion of subjects who initiate the intervention among all consented subjects; 3) *per protocol completion rate* defined as the proportion of subjects who complete 5 or 6 sessions of intervention among those who start the intervention; 4) *intent-to-treat completion rate* defined as the proportion of subjects who complete 5 or 6 sessions of intervention among all randomized subjects. The 95% CI (based on normal approximation or exact binomial test when appropriate) will be estimated for all these rates for overall and by each intervention group. The rates for the RBSTE and PCT groups will be compared by Fisher's exact test. Multivariable analysis will be also performed to examine the difference in outcomes between intervention groups using logistic regression.

**Aim 2:** *To understand Veterans' views of the acceptability and appropriateness of treatment content, the feasibility of participation, and perceptions of provider behavior and attitudes.*

The AIM, IAM, FIM and Provider Rating Scales will be estimated by mean, SD and 95% CI. Intervention groups will be compared by Wilcoxon rank sum test. Multivariable analysis will be also performed to examine the difference in outcomes between intervention groups using linear regression.

**Aim 3:** *To optimize the strategy for holistic evaluation of intervention effects.*

As aforementioned, we will include a comprehensive list of cardiometabolic, neuroendocrine, and inflammatory markers that had been shown as reliable markers of AL in the literature to derive an AL index for each participant. We hypothesize that AL index at baseline will be associated with perceived discrimination as well as other psychosocial outcomes and that pre to post-intervention changes of AL index will differ between the two groups. We will perform regression analysis and variable selection using LASSO (Tibshirani 1996) to identify a smaller subset of the AL markers at baseline that show significant associations with psychosocial outcome measures. The effect size for pre and post change in AL markers will be estimated. This will inform future efficacy and effectiveness studies in potential reduction of a list of biomarkers to enhance feasibility, efficiency and reduce participant burden.

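### Table 1 uses 48 and 24 as denominators for rates they do not fit (enrollment, per-protocol completion), and it labels Wilson widths as exact

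*Combined protocol and SAP*

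**What the plan says.** The Sample size section plans for 8 groups of about 6, "leading to a total sample size of approximately 48 (24/cell) in the 15-month recruitment period". It then offers Table 1 as the precision calculation: "We considered a range of target rate from 0.60 to 0.90", and the plan "estimated the width of the 95% exact binomial confidence interval for enrollment and completion rates for overall and for each intervention group". The table has one row for n = 48 and one for n = 24. The text works through one rate only, initiation: "if an estimated intervention initiation rate is 0.80, a sample size of 48 (total) and 24 (per intervention group") give widths of 0.222 and 0.308.

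The Analyses section, Aim 1, defines four rates, each with its own denominator:

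- Enrollment: "defined as the proportion of consented subjects among all screened and eligible patients".
- Initiation: those who start, out of those who consented.
- Per-protocol completion: completers, out of those who start. The section on acceptability, appropriateness and feasibility uses the same denominator ("the proportion of subjects who complete 6 or more sessions among those who initiate treatment") and sets the success level at 90%.
- Intent-to-treat completion: completers, out of all randomized, with a target of 80%.

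The Recruitment feasibility paragraph defines enrollment rate differently, as the number of contacts needed for each enrollment, and sets no target for it.

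**The concern.** Table 1 is the plan's only precision calculation for its feasibility rates, and feasibility is the purpose of the trial. A binomial interval width means something only if n is the denominator of the rate. The table names enrollment and completion together and applies 48 and 24 to both. Yet 48 is the number enrolled: it sits on top of the enrollment fraction, and it exceeds the per-protocol denominator whenever some participants never start. A reader who takes the table at face value would misjudge the precision of enrollment, and would expect somewhat more precision than the trial can give for per-protocol completion, the rate with the strictest success level.

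**Working it through.** **Inputs.** 48 enrolled, 24 per arm, and rates of 0.60 to 0.90 (Sample size). Two-sided 95% intervals ("A two-sided type I error of 0.05 was assumed"), so z = 1.96 and z² = 3.8415. Rate definitions from Analyses, Aim 1. Assumptions: enrolled = consented = randomized = 48, and initiation of 0.80 to 0.90. The plan gives no expected initiation rate; these two values are its own illustrations.

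**Step 1: reproduce Table 1.** The Wilson score interval without continuity correction has

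width = 2z·√[p(1−p)/n + z²/(4n²)] / (1 + z²/n).

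At p = 0.80, n = 48: 3.92 × √(0.003333 + 0.000417) / 1.0800 = 0.222, as stated. All 14 cells agree to within 0.0005, so 48 and 24 were used as denominators throughout.

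The exact (Clopper-Pearson) interval, which is the method named, does not reproduce the table:

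| Rate | n = 48 stated | n = 48 exact | n = 24 stated | n = 24 exact |
|---|---|---|---|---|
| 0.60 | 0.267 | 0.290 | 0.365 | 0.410 |
| 0.80 | 0.222 | 0.242 | 0.308 | 0.346 |
| 0.90 | 0.174 | 0.189 | 0.249 | 0.276 |

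Over all seven rates, exact widths are about 9% larger at n = 48 and 11-12% larger at n = 24. The normal approximation does not match either (0.277 at 0.60 and 0.170 at 0.90 for n = 48).

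**Step 2: enrollment.** If 48 consent at rate p, the number screened and eligible is 48/p. At p = 0.60, n = 80: 3.92 × √(0.003000 + 0.000150) / 1.0480 = 0.210.

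| Rate | n = 48/rate | Wilson width | Stated | Ratio |
|---|---|---|---|---|
| 0.60 | 80.0 | 0.210 | 0.267 | 0.79 |
| 0.70 | 68.6 | 0.212 | 0.251 | 0.85 |
| 0.80 | 60.0 | 0.200 | 0.222 | 0.90 |
| 0.85 | 56.5 | 0.186 | 0.201 | 0.92 |
| 0.90 | 53.3 | 0.165 | 0.174 | 0.95 |

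With exact intervals and the same denominators, the widths are 0.224 at 0.60, 0.201 at 0.85 and about 0.178 at 0.90. The last two are no narrower than the table.

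The n = 24 row has no meaning for enrollment. Cohorts are randomized after consent and baseline, so eligible Veterans who decline never belong to an arm.

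**Step 3: per-protocol completion.** The denominator is 48 (or 24) times the initiation rate. At p = 0.90 with initiation 0.80, n = 38.4: 3.92 × √(0.002344 + 0.000651) / 1.1000 = 0.195.

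| Initiation (assumed) | n overall / per arm | Wilson width at rate 0.90, overall / per arm | Wider than stated |
|---|---|---|---|
| 0.80 | 38.4 / 19.2 | 0.195 / 0.279 | 12% |
| 0.90 | 43.2 / 21.6 | 0.184 / 0.263 | about 5% |
| 1.00 | 48 / 24 | 0.174 / 0.249 | none |

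At rate 0.80 with initiation 0.80 the widths are 0.247 and 0.342, against 0.222 and 0.308.

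**Step 4: initiation and intent-to-treat completion.** Under the assumption above the denominators are 48 and 24, so the table's n is right and only the interval label is at issue.

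**The case against.** A reader might infer that Table 1 is wrong throughout, too wide for one rate and too narrow for another. The documents do not support that. The only rate the text interprets is initiation, and its denominator is correct. Intent-to-treat completion is also correct if everyone enrolled is randomized. Two of the four rates therefore have the right n. This stands, and it limits the point to enrollment and per-protocol completion.

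The enrollment error has little practical weight. There is no target enrollment rate, and on the Wilson scale the table errs on the cautious side. This also stands, though the cautious direction is not general: on the exact scale that the plan names, it disappears at rates of 0.85 and 0.90.

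The 12% figure for per-protocol completion depends on initiation of 0.80. With per-protocol completion of 0.90, that gives intent-to-treat completion of 0.80 × 0.90 = 0.72, short of the plan's 80% target. The two targets together imply initiation of 0.80/0.90 = 0.89. Then n is about 43 and the width is 0.185 against 0.174, about 6% wider. This is fair, and 12% should be read as the unfavourable end of a range.

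Finally, the sample size rests on group logistics and may vary ("potential range 24-60"). At rate 0.90 the Wilson width runs from 0.249 at n = 24 to 0.155 at n = 60, a much larger swing than the denominator correction. The success levels are set on observed rates, not on confidence limits, so no decision rule turns on the table. What survives all this is that the table names rates its denominators do not fit, and a method it did not use.

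**Conclusion.** The point holds, within limits. For enrollment as Aim 1 defines it, the stated overall widths are too large on the table's own Wilson scale: the right ones are 5% (rate 0.90) to 21% (rate 0.60) narrower. The per-arm row does not apply. For per-protocol completion at rate 0.90, the right widths are about 5% larger than stated if initiation is 0.90 and 12% larger if it is 0.80, with no error if everyone starts. Independently of the denominators, every cell is a Wilson width under an exact label, which understates exact widths by 0.015 to 0.023 at n = 48 and 0.027 to 0.045 at n = 24. That affects the initiation and intent-to-treat entries too.

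These figures assume that 48 is at once the number enrolled, consented and randomized, and they take initiation of 0.80 to 0.90 as an assumption. It would be tempting to conclude that the sample size is inadequate or that the success levels need revision. Neither follows: the plan does not derive 48 from these widths, and its success levels do not refer to them.

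**What to change.** Replace Table 1 with one block per rate:

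- Enrollment: n = 48/rate, overall only.
- Initiation and intent-to-treat completion: n = 48 and 24, stating the assumption that all enrolled are randomized.
- Per-protocol completion: n = 48 and 24 multiplied by a stated initiation assumption, shown at 0.80 and 0.90.

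Either recompute every entry with the exact method or relabel the table as Wilson score, and use the same method in the Aim 1 analysis, which at present allows a normal approximation or an exact interval. Reconcile the two definitions of enrollment rate first: contacts per enrollment is not a binomial proportion, and no interval in Table 1 could describe it.

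The cost is one recalculated table and a few sentences. Stated per-protocol precision becomes slightly less favourable, and if exact intervals are kept so does that of initiation and intent-to-treat completion. Design, sample size and success levels are untouched.

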As a feasibility study, the sample size was not projected to ensure enough study power for hypothesis testing. We assessed the effect size of the outcome (such as Brief PHI, DASS-21, TSDS) that can be detected with the planned sample size and 80% power. The effect size for change in outcome from baseline to post treatment in each intervention group and overall was estimated based on a paired t-test. With a sample size of 24 per group and 48 in total, we could detect an effect size of 0.60 and 0.41, which are moderate effect sizes. To compare the outcome change between the RBSTE and PCT groups, with 24 per group, we could detect a moderate effect size of 0.83 for the difference with 24 subjects per group. This effect size would be clinically meaningful thus signaling the need for additional study.

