**Analyses.** The study has the goals of evaluating the viability and methodology of an RCT comparing two approaches to addressing race-based stress and trauma in VOC. Kraemer and colleagues (2006) have highlighted important limitations of effect sizes generated by pilot studies due to the large standard error. As a result, we will focus our analyses on examining feasibility and generating hypotheses for further examination. Descriptive statistics will be used to summarize the variables as well as to detect outliers, manage missing data and identify data entry errors. Wilcoxon rank sum test and Fisher's exact test will be used to assess the effectiveness of the randomization procedures by comparing baseline variables for participants between two intervention conditions. The primary analysis will be conducted for overall, and for each intervention group, respectively. The comparison of outcomes between intervention groups will be performed when it is necessary and appropriate. Multivariable analysis (logistic regression and linear regression) will be performed when it is appropriate. The associations between patient characteristics and other clinically important baseline variables with the study outcomes will also be assessed using univariate tests. Variables that are significantly associated with the study outcome (assessed by univariate test) or significantly different between study groups with  $p < 0.15$  will be included as potential covariates in the multivariable model. Backward elimination will be used to select the variables, and variables with  $p < 0.10$  will be retained in the final model. For the linear regression model, the outcome variable will be transformed if normal assumption of residuals is not satisfied.

**Aim 1:** *To examine the feasibility of recruiting VOC for an RCT comparing RBSTE and Present Centered Therapy (PCT) for management of stress related to discrimination experiences.*

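### Between-arm clinical contrasts are framed on pre-post change, and adjustment for each measure's own baseline is left to data-driven selection instead of being pre-specified

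*Combined protocol and SAP*

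**What the plan says.** All places are in the combined protocol and SAP, under Research Design and Methods.

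- **Sample size.** The between-arm sentence opens "To compare the outcome change between the RBSTE and PCT groups" and concludes "we could detect a moderate effect size of 0.83 for the difference with 24 subjects per group". The outcomes named as examples are Brief PHI, DASS-21 and TSDS. The section adds that an effect of this size would be clinically meaningful and would point to further study.
- **Analyses, Aim 3.** The hypothesis is that "pre to post-intervention changes of AL index will differ between the two groups". No baseline adjustment is mentioned, and no between-arm model is named for Brief PHI, DASS-21 or TSDS.
- **Analyses, general paragraph.** Arm comparisons and multivariable regression are both conditional on being judged appropriate. Variables associated with the outcome, or differing between arms, at p<0.15 "will be included as potential covariates in the multivariable model". Backward elimination then keeps those with p<0.10. A measure's own baseline has no protected place.
- **Research design.** A cohort of 4-10 Veterans completes the baseline assessment before it is randomized as a unit, so a pre-randomization value of every pre-post measure is due on each participant.

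**The concern.** A change score subtracts the whole baseline value. When the pre-post correlation r is below 1, that is more than regression on baseline would remove. The excess adds noise and pushes the arm difference in the opposite direction to any chance baseline difference. With about eight randomized cohorts, such differences are to be expected.

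The selection rule creates a second problem. Whether baseline is in the model would depend on p-values in a sample of about 48. Brief PHI, DASS-21, TSDS and the allostatic load index could each be analysed differently, with standard errors and intervals that are not comparable. This matters in a pilot meant to settle the methods of a later trial. The Analyses section itself names large standard errors as the weakness of pilot effect sizes.

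**Working it through.** **Inputs from the plan.** "A two-sided type I error of 0.05 was assumed"; effects are those "that can be detected with the planned sample size and 80% power"; enrollment is planned as four groups per arm of about six, "leading to a total sample size of approximately 48 (24/cell) in the 15-month recruitment period".

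**Assumed.** The plan gives no pre-post correlation, so r is varied from 0.3 to 0.9. SDs are taken as equal at both times and members as independent, except where stated.

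**1. Reproduce the plan's figures.** The plan states: "With a sample size of 24 per group and 48 in total, we could detect an effect size of 0.60 and 0.41". Paired t-tests give 0.597 (n = 24) and 0.413 (n = 48). A two-sample t-test with 24 per arm and 46 df gives 0.826, against 0.83 stated; power at 0.83 is 80.4%. The between-arm figure is therefore the unadjusted one, read in SD units of change (the plan does not state the unit).

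**2. Variance.** With s the common SD:

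- change: 2(1 − r)s²
- post value given baseline: (1 − r²)s²
- ratio: (1 − r²) / [2(1 − r)] = (1 + r)/2

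Estimating the baseline slope costs one df (46 to 45) and multiplies the variance by about 1 + 1/44 = 1.023. The last three columns below include that cost; the first does not.

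| r | Variance cut, 1 − (1+r)/2 | Detectable difference, change (baseline SDs) | Detectable difference, adjusted (baseline SDs) | Adjusted, in SDs of change (vs 0.83) | Power where change has 80% |
|---|---|---|---|---|---|
| 0.3 | 35% | 0.98 | 0.80 | 0.67 | 93% |
| 0.5 | 25% | 0.83 | 0.72 | 0.72 | 89% |
| 0.7 | 15% | 0.64 | 0.60 | 0.77 | 85% |
| 0.9 | 5% | 0.37 | 0.36 | 0.82 | 81% |

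A simulation of 20,000 trials per r agreed on power. Once the 1.023 factor is charged, the gain disappears where (1 + r)/2 × 45/44 = 1, that is at r = 88/45 − 1 = 0.956.

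**3. Chance imbalance.** One standard error of the baseline difference is √(2/24) = 0.289 SD. Given a baseline difference D, the change estimate shifts by (r − 1)D, and an analysis of the post value alone shifts by rD. For D = 0.289:

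| r | Change | Post value alone |
|---|---|---|
| 0.3 | −0.20 | +0.09 |
| 0.5 | −0.14 | +0.14 |
| 0.7 | −0.09 | +0.20 |

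The opposite signs show that change over-corrects while ignoring baseline under-corrects. Both shifts average to zero over repeated randomization.

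**4. The plan's selection route.** The simulation took change as the outcome and baseline as a candidate under the p<0.15 and p<0.10 rules. Baseline was kept in 99.7%, 97%, 84%, 68% and 43% of trials at r = 0.3, 0.5, 0.7, 0.8 and 0.9. This presumes that the regression is run and that baseline is offered to it; the plan guarantees neither.

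**5. Cohorts.** With six per cohort and an assumed intracluster correlation of 0.05, the variance factor is 1 + 5 × 0.05 = 1.25. The standard error of the baseline difference becomes √(2/24 × 1.25) = 0.32 SD. The detectable effect on change becomes 0.92 with 46 df, or 1.09 with the 6 df that eight cohorts leave. Baseline adjustment alone does not address this.

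**The case against.** The strongest reply is that the plan never specifies an unadjusted analysis. The 0.83 is a sample-size statement, the allostatic load sentence is a hypothesis, and regressing change on arm plus baseline gives the same arm estimate as regressing the post value on arm plus baseline. The Analyses section allows covariate-adjusted linear regression, and in the simulation its rules usually keep baseline where adjustment matters most. This stands: a reader might infer that the plan commits to unadjusted change, and the text does not support that. What remains is that adjustment is not pre-specified and depends on the data.

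A reader might also infer that baseline imbalance goes uncorrected, or that change scores are biased. Neither holds. Change removes all of the baseline and somewhat too much; the shifts above are conditional on an observed imbalance; and the plan admits covariates that differ between arms at p<0.15.

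The plan also says that the study is not powered for hypothesis tests and seeks signal and feasibility, with primary analyses overall and within each arm. That lowers the priority but does not remove the point, because the plan still gives the between-arm effect a role in judging whether further study is needed.

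**Conclusion.** The point holds as a gap in pre-specification with a modest cost in precision. Nothing in the feasibility aims is invalidated.

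The variance cut of 35% to 5% over r = 0.3 to 0.9 compares always adjusting with never adjusting, so it is an upper contrast. The expected gain over the selection route is smaller, and the gain from adjustment itself is slight when r is 0.8 or more. The figures rest on assumed r, equal SDs and independent members. They carry over less directly to the allostatic load index, a 0-10 count of upper-quartile indicators. It would also go too far to call the adjustment free: it has a small cost, and a model that ignores cohorts would still give an interval that treats 48 people as independent.

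**What to change.** In Analyses, in the general paragraph and under Aim 3, state that every between-arm comparison of a measure taken before and after treatment (questionnaires, allostatic load index, individual markers):

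- regresses the post value on arm, with the same measure's baseline value always in the model and exempt from the p<0.15 screen and backward elimination;
- accounts for the randomized cohort in the same model;
- reports the adjusted difference with its 95% CI, labelled exploratory.

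The Sample size section can keep 0.83 if it is described as the figure for unadjusted change with independent participants.

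Cost: SAP wording, plus one degree of freedom and about 2% in variance per model at the participant level. If the analysis is done on cohort summaries, a covariate would use one of about six degrees of freedom, so the adjustment is better made at the participant level within a model that handles cohort. No new data or visits are needed.
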